6.1.1.2 GAS pyoderma

Pyoderma is a an umbrella term for any form of pyogenic (pus-forming) skin infection including impetigo, ecthyma, carbuncle, folliculitis and tropical ulcer. Similarly to pharyngitis there are many infectious and non-infectious causes of pyoderma, but the most common causes are infection with *Staphylococcus aureus* and GAS.

For the purpose of this study it is necessary to distinguish between:

1. **Asymptomatic colonisation** of the skin with GAS and **symptomatic infection** of the skin by GAS
and
2. **Symptomatic infection** of the skin **by GAS** and **symptomatic inflammation** of the skin **by another infectious or non-infectious cause**

However, with the case of normal skin swabs compared to pyoderma, the sampling site plays a significant role in the diagnosis. Therefore, we will use the following definitions:

Asymptomatic skin GAS colonisation

GAS identified on culture from a swab taken from the normal skin of a participant who at the time of sampling at the sampling site did not have the following features: *pain or itching and pus or crusts with inflammation or erythema.*

GAS pyoderma

GAS identified on culture from a swab taken from a pyoderma-like lesion of a participant which did have the following features: *pain or itching and pus or crusts with inflammation or erythema.*

Pyoderma from a non-GAS cause

GAS not identified on culture from a swab taken from a pyoderma-like lesion of a participant which did have the following features: *pain or itching and pus or crusts with inflammation or erythema*.

6.1.1.3 Invasive GAS disease

Due to the procedures put in place by this study to identify superficial GAS infections (as described in section 5.3.4) and to treat them (as described in section 6.1.3 below), it is unlikely that a GAS infection should progress to an invasive infection. However, it is possible that a participant reports to the study team or is made aware to the study team by another means who is suffering from symptoms consistent with an invasive GAS infection. Invasive GAS infection is usually associated with particularly virulent strains, and in HIC is more common in those with immunosuppression, diabetes and intravenous drug users. Invasive GAS infection usually refers to infections in which patients are systemically unwell, and GAS is identified in a normally sterile area of the body such as blood (GAS septicaemia), lungs (GAS pneumonia), deep muscle or fat tissue (GAS necrotising faciitis), or cerebrospinal fluid (GAS meningitis). A particular clinical syndrome can occur with GAS called Streptococcal toxic shock syndrome (STSS) resulting from bacterial production of exotoxins and virulence factors resulting in a cytokine cascade and the sudden onset of shock, organ failure and frequently death.

For the purposes of this study the following definition will be used:

Invasive GAS infection

GAS isolated from a normally sterile body site, including but not limited to: blood, deep muscle or fat tissue, CSF, joint fluid or pleural effusion, in a participant exhibiting any symptoms of a systemic inflammatory response syndrome or other symptoms compatible with a systemic infection.

6.1.1.4 Acute rheumatic fever (ARF)

Acute rheumatic fever is an inflammatory reaction that occurs in response to a GAS infection, classically understood to develop 2-4 weeks following an episode of GAS pharyngitis, typically in children aged 5-14 years. If left untreated, GAS pharyngitis is more likely to trigger an episode of ARF. As we will treat cases of GAS pharyngitis with antibiotics, it is less likely that episodes of ARF will occur in our cohort.

The Revised Jones Criteria are used as an international standard for diagnosing ARF, and will be used in this study. The criteria can be seen in the appendix. It may be possible within the context of this study to identify the preceding GAS infection, but this is not necessary for the diagnosis of ARF. Although not included in the criteria, a GAS positive pharyngeal swab, and raised streptococcal antibody titre can support the diagnosis.

For the purposes of this study the following definition will be used:

Acute Rheumatic Fever

A participant presenting with 2 major manifestations, or 1 major and 2 minor manifestations of ARF according to the Revised Jones Criteria (see appendix).

6.1.2 Procedure for assessing participants for GAS infection

All enrolled participants will be provided with an on-call number to call at any time when they, or another enrolled household member, is experiencing symptoms that could be compatible with any of the above GAS infections outlined in section 6.1.1. The on-call number will be staffed by a study

nurse 24 hrs a day for the duration of the study, according to an on-call rota. The study nurse taking the call will complete a rapid assessment proforma over the phone, and based on the findings, and in discussion with the on-call study physician if necessary, will make an assessment about the required timeliness for the participant to be assessed in person.

As described in section 5.3.4, the result of the rapid assessment could include an appointment to be seen the next working day, an urgent appointment the same day, evening or night, or an urgent assessment at the MRCG clinical services department.

At any urgent, or non-urgent assessment, the required study samples and CRFs will be completed only when they can safely be done so by not delaying necessary medical treatments or investigations. If in the course of the assessment, it becomes clear to the assessing nurse or physician that the diagnosis is not, or is unlikely to be due to GAS infection, they will continue to assess and manage the patient to the highest available standard of care according to WHO or local guidelines as appropriate, and will then refer on the participant to the appropriate healthcare setting for ongoing care and follow-up.

6.1.3 Management and treatment of GAS infections

The proof of presence of GAS infections requires the culture results to be completed, which may have a delay of several days, depending on culture turnaround time. Therefore it will be necessary to treat GAS infections empirically in the first instance awaiting the culture result.

For acute pharyngitis, treatment will be provided according to WHO guidelines or local guidelines as appropriate.

Pyoderma cases will be treated empirically with cloxacillin or an appropriate alternative according to best local practice and availability, as although they may not be due to GAS, another bacterial cause warrants antibiotic treatment nonetheless.

Any participant presenting with symptoms suggestive of systemic infection and possible invasive disease will be urgently referred to MRCG clinical services department (CSD) where they will be treated by CSD staff according to MRCG guidelines and best practice.

6.2 Management of other medical problems

In the course of the scheduled study visits, and the participant self-referrals for unscheduled visits, it is likely that participants will present with conditions unrelated to GAS infection, but nonetheless require appropriate management. Participants presenting with medical conditions of concern will be treated or referred as appropriate.

6.2.1 Other study related diagnoses

Other diagnoses that will be captured in the study that may be picked up during the examination include scabies, fungal skin infections, and insect bites.

6.2.2 Non-study related diagnoses

All other non-study related diagnoses will be managed or referred on by the study nurses as appropriate according to best local practice. In particular however, unnecessary antibiotic treatment will be avoided, and where there is doubt, the on-call study physician will be consulted. Any fever will be investigated with a malaria RDT in the first instance, and any participant presenting with symptoms meeting the criteria for COVID-19 testing will be referred to the MRCG CSD for appropriate investigation, isolation and management.

7 Discontinuation criteria

7.1 Participant's premature termination

Any participant may withdraw their consent to participate in the study at any point in their enrolment without giving a reason why. If a participant does withdraw their consent, they will be asked whether any data or samples already collected can be used in the analysis or not. An individual household member withdrawing their consent and terminating their involvement will not require the entire household to be withdrawn from the study, but if a majority, or a substantial number of individuals from the same household withdraw, a decision will be made by the PI, study team and co-investigators as to whether the household should be withdrawn.

7.2 Study discontinuation

In the event that the study can no longer continue safely due to any reason, such as MRCG limiting research activities or The Gambia Government introducing new public health restrictions which make the study unable to continue, the study will be discontinued following a decision by the PI, study team and co-investigators.

8 Statistical considerations

The primary outcome measures used to determine sample size were:

1. GAS carriage prevalence, and
2. GAS carriage incidence over 12 months.

In HIC, GAS pharyngeal carriage prevalence in children is 2-17%(12, 13), and in Uganda is 15.9% (29). Our study also includes adults, in whom carriage is lower, but will use pooled skin and pharyngeal carriage as our outcome measure, which will likely increase prevalence in turn. **We therefore estimate a pooled prevalence of 15%.**

GAS pharyngeal carriage yearly incidence in children in the US was shown to be 27-32% (12). We found a skin infection incidence of 592/1000 child years in The Gambia during an influenza vaccine study follow-up (unpublished data) and of which ~50% are likely due to GAS (30). As we are including adults with a likely lower incidence, **we estimate a yearly incidence of 20%.**

The sample size was calculated for the primary objective, GAS carriage prevalence, using the formula below to measure the estimated prevalence of 15% with a precision of $\pm 5\%$.

[figure not shown]
$$n = \frac{Z_{\alpha/2}^2 \times p \times (1 - p)}{e^2}$$

Where p is predicted proportion and e is desired precision.

Using $Z=1.96$ for $\alpha=0.05$, $p=0.15$ and $e=0.05$ we require a sample of 196. Intracluster correlation is unknown, **therefore we used a conservative design effect of 2**, which allowing for 10% drop-out rate gives a required sample size of 431.

We therefore propose to recruit 45 households, which with an average household size of 10, will equal approximately 450 individuals for the main cohort.

This sample size would provide adequate power for precise estimates of prevalence and incidence of GAS carriage and to detect risk factors for GAS carriage (Figures E-G).

Sample size simulations. E: Assuming a design effect of 2, the selected sample size of n=444 would have precision of between ± 4 and $\pm 5\%$ to detect a GAS carriage prevalence of 15%. F: The selected sample size of n=444 would have $>80\%$ power to detect risk factors associated GAS carriage with prevalence or risk ratios of 2, 2.5 and 3. G: The sample size would have a precision of between ± 4 and $\pm 5\%$ to detect a GAS carriage incidence of 20% per person year.

9 Data handling and record keeping

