2.1 Study endpoints**Primary endpoints:**

- Asymptomatic GAS throat and skin carriage and clinical GAS infection prevalence at each monthly visit
- Asymptomatic GAS throat and skin carriage and clinical GAS infection incidence per person year
- Duration of asymptomatic GAS throat and skin carriage to the nearest week
- Phylogenetic relatedness of GAS isolates by whole genome sequencing
- Clinical examination findings and features of clinical GAS infection

Secondary endpoints:

- Presence of risk factors for GAS carriage or disease at individual and household levels
- Seasonal variation in GAS carriage and infection prevalence
- GAS *emm* type
- Groups C and G streptococcal prevalence and incidence
- Quantification of bacterial presence by qPCR
- GAS serological responses (including seroprevalence and fold-change in antibody titres in response to asymptomatic carriage and clinical infection).
- GAS presence on household swabbing and settle plates
- GAS antimicrobial sensitivity

3 Study design

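### The 15% prevalence and 20% yearly incidence assumptions are not reconciled with each other, and the stated ±4 to ±5% incidence precision is met only without the protocol's own design effect of 2

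*Protocol*

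**What the plan says.** Section 8 names carriage prevalence and 12-month carriage incidence as the two measures behind the sample size.

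- **Prevalence.** It cites 2-17% for throat carriage in children in high-income countries and 15.9% in Uganda. It notes that adults carry less and that pooling skin with throat will push the figure up. It concludes: "We therefore estimate a pooled prevalence of 15"%.
- **Incidence.** It cites 27-32% a year for throat carriage in US children, and 592 skin infections per 1000 child-years in The Gambia, about half of them likely due to group A streptococcus. The only adjustment described is downward, for adults. It concludes: "we estimate a yearly incidence of 20"%.
- **Precision.** For prevalence, the simulation caption says: "Assuming a design effect of 2, the selected sample size of n=444 would have precision of between" ±4 and ±5%. For incidence (panel G), it claims the same ±4 to ±5% "to detect a GAS carriage incidence of 20% per person year". A design effect is named for panel E but not for panel G. The panels themselves are not available to this review.
- **Sample size.** The section says "we require a sample of 196" for prevalence, "therefore we used a conservative design effect of 2", and "allowing for 10% drop-out rate gives a required sample size of 431".
- **Duration.** Section 2.1 lists as a primary endpoint "Duration of asymptomatic GAS throat and skin carriage to the nearest week". Sections 3.2.2 and 5.3.6 swab new carriers weekly until two consecutive negatives. No expected duration is given anywhere.

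**The concern.** Prevalence, incidence and mean duration are linked, so fixing any two fixes the third. The protocol fixes prevalence and incidence from different sources and does not look at what they imply for duration, which the study sets out to measure. The adjustments are also uneven: including adults is said to lower both figures, but pooling two body sites is credited only to prevalence. Prevalence therefore stays near the top of its cited range, while incidence falls below both of its cited inputs.

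What is at stake is the stated precision for incidence, a primary endpoint. That statement depends on the rate being as low as 0.20 and, as shown below, on ignoring the household clustering that the same section allows for in prevalence.

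**Working it through.** **Inputs (protocol Section 8 and simulation caption).** P = 0.15; I = 0.20 per person-year; n = 444; design effect (DE) = 2; Z = 1.96. Follow-up is 12 months, so 444 people give at most 444 person-years (PY). One year = 52.18 weeks.

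**1. The plan's own figures.**
- Sample size: 1.96² × 0.15 × 0.85 / 0.05² = 195.9, so 196. Then 196 × 2 = 392, and 392 × 1.10 = 431.2. This matches 431.
- Panel E, prevalence with DE 2: 1.96 × √(2 × 0.15 × 0.85 / 444) = ±4.7 points. This matches.
- Panel G, incidence without a design effect (Poisson): 1.96 × √(0.20 / 444) = ±4.2 points. If only 85% of person-years are at risk (377.4 PY), it is ±4.5. Both match the stated ±4 to ±5.

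**2. Panel G with the design effect of 2, still at 0.20.**
- Binomial, 444 people: 1.96 × √(2 × 0.20 × 0.80 / 444) = ±5.3 points.
- Poisson, 444 PY: 1.96 × √(2 × 0.20 / 444) = ±5.9 points.
- Poisson, 377.4 PY at risk: 1.96 × √(2 × 0.20 / 377.4) = ±6.4 points.

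All three fall outside the stated range.

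**3. Duration implied by the two planning figures (steady state).**

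| Reading of 20% | P/(1−P) = I × D | P = I × D |
|---|---|---|
| Rate of 0.20 per PY | 0.1765 / 0.20 = 0.882 y = 46.0 weeks | 0.15 / 0.20 = 0.75 y = 39.1 weeks |
| One-year risk, rate = −ln(0.80) = 0.223 | 0.1765 / 0.223 = 41.3 weeks | 0.15 / 0.223 = 35.1 weeks |

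The range is 35 to 46 weeks.

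**4. If 15% prevalence holds and carriage is shorter.** The protocol gives no duration, so these durations are assumptions. I = 0.1765 / D; half-width = 1.96 × √(DE × I / 444).

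| Mean carriage | Rate per PY at risk | Half-width, no DE | Half-width, DE 2 | DE 2 half-width ÷ rate |
|---|---|---|---|---|
| 46 weeks | 0.20 | ±4.2 points | ±5.9 points | 29% |
| 26 weeks | 0.35 | ±5.5 | ±8 | 22% |
| 12 weeks | 0.77 | ±8 | ±12 | 15% |
| 8 weeks | 1.15 | ±10 | ±14 | 12% |

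Using only the 85% of person-years at risk widens each half-width by a factor of 1/√0.85 = 1.08.

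**5. If 0.20 per PY holds instead.** P = I × D / (1 + I × D). Carriage of 4, 8, 12 or 26 weeks then goes with prevalence of 1.5%, 3.0%, 4.4% or 9.1%.

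**6. Can the cited sources settle it?** In the same odds form, 2% with 32% gives 0.0204 / 0.32 = 3.3 weeks, and 17% with 27% gives 0.2048 / 0.27 = 39.6 weeks. A span of about 3 to 40 weeks does not identify the wrong input.

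**The case against.** The case for leaving the text alone is a fair one. The sample size was calculated for prevalence, so 196, 431 and 45 households do not depend on the 20%. The checked figures reproduce, and the panel G caption does not say that a design effect was used. The 46 weeks is the top of the range, and it assumes steady state in a study that expects seasonality. A higher rate would also bring more events, so incidence would be estimated better in relative terms. All of this stands. It limits the point to the incidence figure and its stated precision, but it does not explain why clustering within households is allowed for in prevalence and apparently not in incidence.

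A reader might also infer several stronger things that the documents do not support:

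- *That either the incidence precision or the weekly duration sub-study must be wrong.* The 15% could be the wrong figure instead. A rate of 0.20 with carriage of weeks simply means lower prevalence (step 5), much of it still inside the cited 2-17%.
- *That the duration sub-study rests on a wrong number.* It rests on no number. Weekly swabbing to two negatives works for any duration, and the nearest week is a measurement resolution, not an assumed length. Long carriage would mean more censoring and more visits.
- *That 20% is unreachable because the two child inputs add to 57-62%.* One input is throat carriage and the other is skin infection. Section 6.1.1 defines carriage and infection as separate outcomes, so they cannot be added.
- *That planned acquisition counts or visit workload are wrong.* The protocol states neither.

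**Conclusion.** The point holds in a limited form. The 15% and 20% are not reconciled: together they imply mean carriage of about 35 to 46 weeks, no duration is stated against which to judge that, and site pooling is credited to only one of them. Which figure is wrong cannot be decided from the protocol.

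The firmer part is the precision statement. At the protocol's own 0.20 and its own design effect of 2, the half-width is about ±5.3 to ±6.4 points, not ±4 to ±5. If 15% prevalence is right and carriage averages 26, 12 or 8 weeks, it is about ±8, ±12 or ±14 points on 444 person-years, with better relative precision.

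The duration argument assumes approximate steady state, and the 8, 12 and 26 weeks are illustrative. The precision argument assumes that a design effect of 2 applies to incidence as it does to prevalence, and that follow-up is complete. The prevalence-based sample size of 431 is unaffected.

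**What to change.** In Section 8 and the simulation caption:

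1. Say whether 20% is a rate per person-year or the share of people who acquire carriage at least once in a year, and state precision on that scale.
2. State an assumed range for mean carriage duration, with its basis.
3. Re-derive either incidence or prevalence so that the two agree over that range, and apply the skin-throat pooling to both.
4. Restate the incidence precision with the design effect of 2 across the range, in absolute and relative terms, and give the person-years used.

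The cost is some text and a small table, plus a less favourable absolute precision for incidence. The number of households, the visit schedule and the total of 431 need not change.

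### The 10% drop-out is added as ×1.1, so the required size should read 436 rather than 431, and the precision and power statements cite a third figure, 444, that the text does not derive

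*Protocol*

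**What the plan says.** Protocol section 8 (Statistical considerations) sizes the study on the precision of the carriage prevalence estimate. The expected pooled prevalence is 15% and the target half-width is 5 percentage points. The steps are:

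- Unclustered size: "Using $Z=1.96$ for $\alpha=0.05$, $p=0.15$ and $e=0.05$ we require a sample of 196".
- Clustering: intracluster correlation is described as unknown, and "therefore we used a conservative design effect of 2".
- Drop-out: "which allowing for 10% drop-out rate gives a required sample size of 431".
- Plan: 45 households averaging 10 members, which "will equal approximately 450 individuals for the main cohort".

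The caption to the sample size simulations in the same section then makes three statements. E (prevalence precision, design effect 2) and F (power for risk factors) are both made for "the selected sample size of n=444". G (incidence precision) refers only to the sample size, without a number.

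**The concern.** A drop-out rate is a fraction of those enrolled. To keep a given number after losing 10%, that number is divided by 0.9. Multiplying by 1.1 gives a smaller figure, which no longer contains the required number once the loss has occurred. The figure 431 has the appearance of the second method.

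There is also a traceability problem. Within one section the required number is 431, the proposed number is about 450, and the number called selected is 444. A reader cannot tell which of these the precision and power statements describe, or whether it is a count before or after drop-out. This section is where the protocol justifies recruiting 45 households, so the chain of numbers should close.

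**Working it through.** **Inputs**, all from protocol section 8: Z = 1.96, p = 0.15, e = 0.05, design effect 2, drop-out 10%, planned size about 450, size in the caption 444.

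**Reproducing the plan's figure**

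1. Unclustered: 1.96² × 0.15 × 0.85 / 0.05² = 3.8416 × 0.1275 / 0.0025 = 195.9, rounded up to 196. This matches the protocol.
2. With design effect: 196 × 2 = 392 people who must provide data.
3. Drop-out by multiplication: 392 × 1.1 = 431.2, stated as 431. This reproduces the protocol.
4. Drop-out by division: 392 / 0.9 = 435.6, rounded up to 436. This does not give 431.

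The choice between 196 and the unrounded 195.92 does not matter. Unrounded, multiplication gives 431.0 and division gives 435.4, which still rounds up to 436.

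**Does 431 deliver its own target?**

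Half-width = 1.96 × √(2 × 0.15 × 0.85 / n) = 1.96 × √(0.255 / n), where n is the number providing data.

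- 431 × 0.9 = 387.9 remaining: half-width 5.03%. This narrowly misses ±5%.
- 436 × 0.9 = 392.4 remaining: half-width 4.996%. This meets it.

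The shortfall at 431 is about 4 people (392 − 388) and 0.03 percentage points. The correction is 5 people, 5/431 = 1.2%.

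**Where 444 and 450 stand**

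| Enrolled | Half-width, no loss | Remaining after 10% loss | Half-width after loss |
|---|---|---|---|
| 444 | 4.70% | 399.6 | 4.95% |
| 450 | 4.67% | 405 | 4.92% |

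Statement E puts the half-width between 4% and 5%. That is true in all four cells. The figure 444 exceeds 431 by 13 and falls short of 450 by 6 (1.3%), and no step in the text produces it.

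**The case against.** The strongest reply is that nothing turns on 431. Recruitment is fixed in households and ends once 45 have consented (section 5.2). The resulting 450 or so exceeds both 431 and 436. A miss of 0.03 percentage points is far smaller than the uncertainty in a guessed 15% prevalence and an assumed design effect. This stands as a statement about consequences. It does not make 431 correct, because the protocol presents it as the size required after allowing for drop-out, and after that drop-out it misses the requirement.

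On 444, the figures behind the caption are not reproduced in the text at hand and may contain its basis. One can note that 400/0.9 = 444.4, but nothing in the protocol says this is the origin. So the criticism is limited to the wording that can be read: a size called selected that differs from the size proposed in the same section.

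A reader might infer three stronger points, which the protocol does not support:

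- **That the study is too small.** The planned 450 meets the ±5% prevalence target even after 10% loss.
- **That statements E to G ignore drop-out.** The text does not say whether 444 is before or after loss, and E holds either way, so E cannot show which was used.
- **That every statement should be restated at 405.** The cohort is open (section 3.1), absent members may enrol at later monthly visits and households may be replaced (sections 4.3 and 5.2). Prevalence is reported at each monthly visit and incidence per person-year (section 2.1). A flat 10% reduction is a reasonable allowance for prevalence late in follow-up, but not clearly the number analysed at enrolment, for risk factors or for incidence.

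**Conclusion.** The required sample size is misstated: 436 rather than 431, from the protocol's own inputs and reading the 10% as a share of those enrolled. Separately, the selected size of 444 agrees with neither the required nor the proposed figure. Both are minor defects of arithmetic and consistency. With design effect 2 and p = 0.15, the planned 450 gives ±4.7% before loss and ±4.9% after, so the prevalence target is met and enrolment need not change.

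The check covers prevalence only. It does not verify the power claim in F or the incidence claim in G. G in particular depends on a method the caption does not state: at 444, a binomial 20% with design effect 2 gives ±5.26%, and a Poisson rate over 444 person-years without a design effect gives ±4.16%.

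**What to change.** In section 8:

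1. Replace 431 with 436 and show the step as 392/0.9.
2. Use one selected sample size, about 450, in statements E, F and G. If 444 is kept, state where it comes from.
3. Say for each statement whether the number is before or after the 10% loss. For prevalence with design effect 2, the wording can be ±4.7% at 450 and ±4.9% with 405 remaining.

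Item 1 and the prevalence part of items 2 and 3 need only a text edit. For F and G, the authors should confirm the claims at the chosen number from their existing simulations and state the method and design effect used. There is no cost in recruitment, procedures or follow-up.

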5.5 Clinical and field evaluations

5.5.1 Socio-demographics and household set-up

At the enrolment and later visits where necessary, a series of questions will be asked of each individual participant in relation to their socio-demographic information including their date of birth, sex, tribal group, education and occupation. Any relevant medical information that is identifiable from ante-natal cards (ANC), or infant welfare cards (IWC) (especially for younger children) will be recorded such as birthweight, previous medical diagnoses and allergies.

For each household data will be collected relating to the household set-up including the number of buildings, number of rooms, accessibility for non-household members, sleeping arrangements, mosquito net use/coverage, household income, water access and proximity to community meeting points.

At subsequent monthly visits, individuals will be asked to briefly update some of their sociodemographic details such as occupation, school attendance and any other factors that may change throughout the year, and to complete any missing data. Similarly, alterations to household set-up will also be collected.

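### Caption F's power above 80% for a ratio of 2 names no design effect; with section 8's own value of 2 it does not hold for household-shared exposures at one visit and 15% prevalence

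*Protocol*

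**What the plan says.** Section 8 (Statistical considerations) says that the intracluster correlation is unknown, and "therefore we used a conservative design effect of 2". It estimates a pooled carriage prevalence of 15%, and for incidence "we estimate a yearly incidence of 20" per cent. It closes by claiming adequate power for precise prevalence and incidence estimates "and to detect risk factors for GAS carriage (Figures E-G").

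The three captions that follow are not alike:

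- Caption E: "Assuming a design effect of 2, the selected sample size of n=444 would have precision" of between ±4 and ±5% at 15% prevalence.
- Caption F: the same n=444 has more than 80% "power to detect risk factors associated GAS carriage with prevalence or risk ratios of 2, 2.5 and 3". No design effect, base risk, exposure share or number of visits is named.
- Caption G: precision of between ±4 and ±5% "to detect a GAS carriage incidence of 20% per person year". No design effect is named.

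Section 2.1 lists as a secondary endpoint "Presence of risk factors for GAS carriage or disease at individual and household levels". Section 5.5.1 collects data on "household set-up including the number of buildings, number of rooms, accessibility for non-household members, sleeping arrangements, mosquito net use/coverage, household income, water access". Several of these, such as number of rooms, household income and water access, take one value for everyone in the household.

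**The concern.** A design effect of 2 halves the effective sample, from 444 to 222. It bears in full on the comparison of exposed with unexposed when the exposure is common to all members of a household. Section 8 brings it in because the clustering is unknown, and caption E uses it. Caption F puts a power figure on the same 444 people without mentioning it.

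Caption F and the sentence that refers to it are the only power statements for risk factors for carriage (secondary objective 1). If a household-level factor shows no association, readers will judge that result against a stated power above 80%. If the protocol's own clustering assumption gives clearly less, the result would be over-read as evidence of no effect.

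**Working it through.** **Inputs from section 8.** n=444; design effect (DE) 2; prevalence 15%; yearly incidence 20%; ratios 2, 2.5 and 3; Z=1.96, carried over to caption F as a two-sided 5% test.

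**Inputs not given.** The exposed share f is swept from 2% to 98%. The text does not say whether the base risk is the overall risk or the risk in the unexposed, so both are computed.

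**Precision captions first.**

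- Caption E: 1.96·√(0.15·0.85·DE/444) = 3.3% with DE 1 and 4.7% with DE 2. The stated ±4-5% needs DE 2.
- Caption G as a proportion: 1.96·√(0.2·0.8·DE/444) = 3.7% with DE 1 and 5.3% with DE 2.
- Caption G as a rate over 444 person-years: 1.96·√(0.2·DE/444) = 4.2% with DE 1 and 5.9% with DE 2. The stated ±4-5% is met as a rate without a design effect and on neither basis with DE 2.

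**Power for caption F.** Two-proportion test with pooled variance under the null and N = 444/DE:

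- p0 = base/(1 + f(RR−1)) if the base is the overall risk, or p0 = base if it is the unexposed risk; p1 = RR·p0
- s0 = √[p̄(1−p̄)(1/(Nf) + 1/(N(1−f)))], with p̄ = f·p1 + (1−f)·p0
- s1 = √[p1(1−p1)/(Nf) + p0(1−p0)/(N(1−f))]
- power ≈ Φ[(p1−p0 − 1.96·s0)/s1]

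The two maxima for ratio 2, DE 2 and 15%:

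- 15% overall, f=0.35: p0=0.1111, p1=0.2222, s0=0.0502, s1=0.0539. Power = Φ[(0.1111−0.0985)/0.0539] = Φ(0.234) = 59%.
- 15% unexposed, f=0.47: p0=0.15, p1=0.30, s0=0.0558, s1=0.0556. Power = Φ[(0.15−0.1093)/0.0556] = Φ(0.732) = 77%.

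| Ratio | Base risk | DE | Power at 10/20/30/40/50% exposed | Maximum | Exposed share giving ≥80% |
|---|---|---|---|---|---|
| 2 | 15% overall | 1 | 65/80/85/86/84% | 86% | about 20-58% |
| 2 | 15% unexposed | 1 | 69/88/94/96/97% | 97% | about 15-82% |
| 2 | 15% overall | 2 | 42/54/59/59/55% | 59% | none |
| 2 | 15% unexposed | 2 | 45/63/72/76/77% | 77% | none |
| 2.5 | 15% overall | 2 | 65/78/81/81/77% | 82% | about 24-42% |
| 2.5 | 15% unexposed | 2 | 71/89/95/97/97% | 97% | about 14-83% |
| 3 | 15% overall | 2 | 81/91/92/91/88% | 92% | about 10-62% |
| 2 | 20% overall | 2 | 53/68/73/73/70% | 74% | none |
| 2 | 20% unexposed | 2 | 57/77/86/90/91% | 91% | about 23-74% |

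Caption F's figure for ratio 2 at 15% is therefore reproduced with DE 1 over a wide range of exposure shares, and at no share with DE 2. Other two-sided tests (unpooled risk difference, log risk ratio, log odds ratio) give DE 2 maxima of 56-59% (overall) and 75-78% (unexposed). The largest design effect that still allows 80% for ratio 2 is about 1.2 (15% overall), 1.85 (15% unexposed), 1.7 (20% overall) or 2.7 (20% unexposed).

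**Exposures that vary within households.** A simulation used 45 households of 10, an intracluster correlation (ICC) of 1/9 (so that 1+9/9=2), one visit, 15% overall and ratio 2. At 20/30/40/50% exposed, power is 45/50/54/56% for an exposure shared by the household and 72/80/84/84% for one not clustered by household. Type I error was 5-9%, highest for shared exposures at 20% exposed, so the shared-exposure figures are if anything too high.

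**Repeated swabs.** For a household-level exposure over 13 visits, with ICC 1/9, persistent share k of the household correlation and extra within-person correlation r, the effective design effect is [1 + 12(k·ICC + r) + 9·ICC + 108·k·ICC]/13.

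- k=1, r from 0 to 0.3: 1.18 to 1.46. Maximum power for ratio 2 is 80.5% down to 72% (15% overall), or 94% down to 88% (15% unexposed).
- k=0.5, same r: 0.67 to 0.94. Maximum power is 96% down to 88% (15% overall).

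k, r and full attendance are assumptions; the protocol gives none of them.

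**The case against.** Caption F mentions neither household-level exposures, nor a single visit, nor 15% prevalence. It speaks of prevalence or risk ratios, and section 8 sizes on both prevalence and 12-month incidence. With 20% as the unexposed yearly risk, ratio 2 passes under design effect 2 at about 23-74% exposed. The study takes up to 13 swabs per person, and joint analysis can restore the power. The panel that might show the inputs is not available. The 77% is close to 80%: an unexposed prevalence of 16% instead of 15% gives 80.2%, and section 8 itself calls the design effect conservative.

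Most of this stands, and it limits the point. A reader might infer that the 80% claim is simply false. The documents do not support that, because readings of section 8 exist on which it holds. A reader might also infer from caption G that caption F was calculated without clustering. G points that way, but carrying design effect 2 over to incidence is an assumption, and how G was calculated does not show how F was. Nor should ratio 2 be confined to unclustered exposures at 30-50% exposed: that range comes from the 15%-overall simulation alone, and 15% unexposed without a design effect gives about 15-82%.

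What the objection does not remove is that the caption makes a flat claim whose truth depends on conditions it does not name. On one natural reading of the protocol's own figures, for a class of exposures it lists, the claim fails at every exposure share. Because the ceilings are maxima over exposure share and cover both meanings of 15%, the missing panel cannot change them for that reading.

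**Conclusion.** The point holds in a limited form. For exposures shared by a household, one visit, 15% prevalence, two-sided 5% and design effect 2, ratio 2 has at most 59% power (15% overall) or 77% (15% unexposed), against a stated figure above 80%. Ratio 2.5 is borderline if 15% is the overall prevalence, and ratio 3 largely stands. On the 20% yearly incidence with the same design effect, ratio 2 fails if 20% is the overall risk (at most 74%) and passes over a wide range if it is the unexposed risk. The shortfall is smaller or absent for exposures that vary within households. It may disappear under joint analysis of the monthly swabs, depending on correlations that the protocol does not give.

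A reader might conclude that the study is too small. That does not follow: the required 431 rests on the precision of the prevalence estimate with design effect 2, and nothing here touches it. This is a correction to the stated power for one secondary objective, worth making because it governs how null household-level results are read.

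**What to change.** Restate caption F, and the section 8 sentence that cites it, with the design effect, base risk (overall or unexposed), exposure share and number of visits used.

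- **Household-level exposures:** give the power or the detectable ratio with design effect 2. For one visit and 15% overall, 80% power is reached at ratios of about 3.0, 2.6, 2.5, 2.5 and 2.6 for 10, 20, 30, 40 and 50% exposed.
- **Ratio 2:** keep the claim for individual-level exposures, or for a repeated-swab or incidence analysis, with the assumptions and exposure range under which it holds. Without a design effect the range is about 20-58% exposed at 15% overall, or 15-82% at 15% unexposed. For repeated swabs, state the household and within-person correlations. For incidence, say whether 20% is the overall or the unexposed risk.
- **Caption G:** either say that no design effect was applied, or give the precision with it (±5.3% as a proportion, ±5.9% as a rate).

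The cost is the rewording of two captions and one sentence, and a less favourable power statement for household-level factors. Sample size, endpoints and procedures stay as they are.
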